6.4.3 Analysis of Exploratory Endpoints

Data of the following explorative endpoints will be summarized, separately, for pediatric subjects:

- Percentage of subjects with a reduction in daytime incontinence episodes (< 50% reduction [non-responder], 50% [partial responder] and 100% [responder])
- Improvement from baseline in worst incontinence grading. Average over 7 days will be calculated of the score of "What was your worst leakage during the day": 1 Slightly Wet; 2 Moderately Wet; and 3 Fully Wet
- Mean number of micturitions per 24 hours, adjusted for fluid intake:
 - Number of micturitions per 24 hours that would be required at week 12/EoT to void the same total volume as voided at baseline
 - Difference in mean number of micturitions per 24 hours adjusted for fluid intake compared to the expected mean number
- Mean volume voided per micturition as a percentage of expected bladder capacity
- Categorized mean volume voided per micturition as a percentage of expected bladder capacity (results and changes from baseline).

Efficacy endpoints for adolescents will be analyzed descriptively.

- Change from baseline at the end of the 12-week treatment period (adolescents only):
 - Mean number of micturitions per 24 hours
 - Mean number of daytime micturitions per 24 hours
 - Mean volume voided per 24 hours

- Maximum volume voided
- Mean number of incontinence episodes per 24 hours
- Number of dry (incontinence-free) days per 7 days at the end of the 12-week treatment period (adolescents only)
- Mean number of daytime grade 3 or 4 on Patient Perception of Intensity of Urgency Scale (PPIUS) urgency episodes per 24 hours (adolescents only) will be summarized by treatment group and visit.

Correlations between the primary endpoint and mean volume voided, as well as incontinence episodes, will be explored. Scatter plots will be presented to access the correlation between the primary end point and mean volume voided and number of incontinence episodes at visit 7/week 12.

6.5 Analysis of Safety

Safety analysis will be conducted on the SAF and conducted separately for children, adolescents and overall. Safety endpoints will be summarized, for each age group and overall, by treatment group and visit, if applicable. Presented will be descriptive statistics.

6.5.1 Adverse Events

Summaries and listings of SAEs and Serious TEAEs include SAEs upgraded by the sponsor based on review of the Sponsor's list of Always Serious terms or upgraded according to the Important Medical Event process, if any upgrade was done.

The coding dictionary for this study will be MedDRA. It will be used to summarize AEs by SOC and PT.

An overview table will include the following details:

- Number of TEAEs
- Number and percentage of subjects with TEAEs
- Number of drug related TEAEs
- Number and percentage of subjects with drug related TEAEs
- Number of serious TEAEs
- Number and percentage of subjects with serious TEAEs
- Number of serious drug related TEAEs
- Number and percentage of subjects with serious drug related TEAEs
- Number of TEAEs leading to permanent discontinuation of study drug
- Number and percentage of subjects with TEAEs leading to permanent discontinuation of study drug
- Number of drug-related TEAEs leading to permanent discontinuation of study drug
- Number and percentage of subjects with drug-related TEAEs leading to permanent discontinuation of study drug
- Number of TEAEs leading to death
- Number and percentage of subjects with TEAEs leading to death
- Number of drug-related TEAEs leading the death

- Number and percentage of subjects with TEAEs leading to death
- Number and percentage of subjects who died.

The number and percentage of subjects with TEAEs, as classified by SOC and PT will be summarized by age group and overall for each treatment group. Summaries will be provided for:

- TEAEs
- Drug related TEAEs
- Serious TEAEs
- Drug related serious TEAEs
- TEAEs leading to permanent discontinuation of study drug
- Drug related TEAEs leading to permanent discontinuation of study drug
- Common (>=5% in Any Treatment Group) TEAEs Excluding SAEs

The number and percentage of subjects with TEAEs, as classified by PT only, will be summarized by age group and overall for each treatment group.

The number of TEAEs and the number and percentage of subjects with TEAEs, as classified by SOC and PT will also be summarized by severity and by relationship to study drug. In the subject count, if a subject has multiple TEAEs with the same SOC or PT, but with differing severity or relationship, then the subject will be counted only once with the worst severity and highest degree of relationship, however, if any of the severity or relationship values are missing then the subject will be counted only once with missing severity or relationship. In the adverse event count, the adverse events will be presented in each category they were classified to. Drug related TEAEs will be presented in a similar way by severity only.

Adverse events of interest will be tabulated by PT.

AEs will be provided in listing format by country, site and subject for the SAF.

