9.5.1 Adverse Events

AEs will be coded using MedDRA. A TEAE is defined as an AE observed after starting administration of the IP and 30 days after the final administration of IP. An IP-related TEAE is defined as any TEAE with a causal relationship assessed as "yes" by the investigator.

The number and percentage of TEAEs, drug-related TEAEs, serious TEAEs, drug-related serious TEAEs, TEAEs leading to leading to withdrawal of treatment and drug-related TEAEs leading to leading to withdrawal of treatment will be summarized by SOC, preferred term, age group and treatment group. The number and percentage of TEAEs by severity will also be summarized. The worst severity will be summarized if the same AE is recorded more than once for a subject.

AE data will be listed.

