12.4.4 Criteria for Defining the Severity of an Adverse Event

The investigator will use the following definitions to rate the severity of each AE:

- Mild: No disruption of normal daily activities
- Moderate: Affects normal daily activities
- Severe: Inability to perform daily activities

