5.4.1 Adverse Events

AEs will be coded using MedDRA. A TEAE is defined as an AE observed after starting administration of the IP until 30 days after the final administration of IP.

If the adverse event occurs on Day 1 and the onset check box on the (AE) eCRF is marked "Onset after first dose of study drug" or the onset check box is left blank, then the adverse event will be considered treatment emergent. If the adverse event occurs on Day 1 and the onset check box is marked "Onset before first dose of study drug", then the adverse event will not be considered treatment emergent. If a subject experiences an event both during the pre-investigational period and during the investigational period, the event will be considered as TEAE only if it has worsened in severity (i.e., it is reported with a new start date).

A drug-related TEAE is defined as any TEAE with at least a possible relationship to study treatment as assessed by the investigator or with missing assessment of the causal relationship.

An AE designated as serious by either the investigator or determined by Important Medical Event process will be summarized as an SAE. However, if the event is on IME list but medical monitor agrees with investigator that event is not SAE, then event can be downgraded.

Common TEAEs are defined as preferred terms (PTs) that have been reported by at least 5% of the subjects in any of the treatment groups.

When an AE start or stop date is missing, the date will be imputed using the rules in Section 6.10.2.2.

Adverse Events of Special Interest

Adverse Events of Special Interest include:

• Abnormal cardiac electrophysiology (including QTc prolongation), cardiac arrhythmia, and other cardiovascular adverse events

- Increased blood pressure as assessed through vital signs monitoring
- Hypersensitivity reactions
- Urinary retention
- Abnormal nervous system events: seizure, syncope, headache and dizziness

AEs of interest will be identified using all Preferred Terms (PT) from Standardized MedDRA queries (SMQ), see Table 2, or sponsor-defined list of search terms, see Appendix 9.2. Note: Most recent MedDRA version in which the AEs are coded will be used.

CV - Increased blood pressure	Hypertension SMQ – Narrow search
CV - QT prolongation	Torsade de pointes/QT prolongation SMQ – Broad search

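### In the by-severity adverse event tables, one ungraded record moves a subject with a severe event out of the severe row and into the missing row

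*SAP*

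**What the plan says.** SAP 6.5.1 plans subject and event counts by severity and by relationship, within SOC and PT. For a subject with several TEAEs in one row and differing values, the basic rule is "then the subject will be counted only once with the worst severity and highest degree of relationship". An exception follows: "if any of the severity or relationship values are missing then the subject will be counted only once with missing severity or relationship". The trigger is any missing value, not all values missing.

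Two further sentences set the reach of the exception. For events rather than subjects, "In the adverse event count, the adverse events will be presented in each category they were classified to", so the exception does not apply there. For the drug-related subset, "Drug related TEAEs will be presented in a similar way by severity only", so the exception does apply to that severity table.

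Protocol 9.5.1 gives its own rule: "The worst severity will be summarized if the same AE is recorded more than once for a subject". It makes no exception for missing grades. The top of the three-point scale in Protocol 12.4.4 is "Severe: Inability to perform daily activities".

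On causality, SAP 5.4.1 defines a drug-related TEAE as "any TEAE with at least a possible relationship to study treatment as assessed by the investigator or with missing assessment of the causal relationship".

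**The concern.** A by-severity subject count should show how many subjects reached each grade. Once a severe event is recorded, an ungraded record in the same row cannot make that subject's worst severity lower than severe. The exception discards the known grade all the same. For the severe row it works in one direction only: it can take subjects out and never put one in.

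Several records per row are to be expected. SOC rows pool different events, and Protocol 7.3.2 has each change in an event's severity entered as a separate AE. An event that worsens therefore leaves at least two records under one PT, which is where the worst grade matters most. If grades are missing equally often in both arms, the arm with more events per subject is the more exposed.

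At stake is the number of children and adolescents shown as having a severe event in a placebo-controlled paediatric safety comparison.

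**Working it through.** The documents give no figure for this rule, so there is nothing to reproduce. I applied the rule to example subjects and then gauged its scale. I read the exception term by term: a missing grade governs the severity table, and a missing causality governs the relationship table.

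**Severity: one subject, one SOC or PT row**

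| Records | SAP 6.5.1 | Worst non-missing grade |
|---|---|---|
| severe, mild | severe | severe |
| severe, missing | missing | severe |
| mild, missing, severe | missing | severe |
| mild, missing | missing | mild |
| missing only | missing | missing |

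The rules differ whenever graded and ungraded records occur together, and in the second and third lines a severe subject is lost from the severe row.

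**How often this could happen.** Take a subject with k TEAEs in the row, one of them severe and graded. Let each of the other k − 1 lack a grade with probability m, independently. The subject is moved to missing with probability 1 − (1 − m)^(k−1). The values of m are assumptions.

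| m | k = 2 | k = 3 | k = 4 | k = 5 |
|---|---|---|---|---|
| 1% | 1.0% | 2.0% | 3.0% | 3.9% |
| 2% | 2.0% | 4.0% | 5.9% | 7.8% |
| 5% | 5.0% | 9.8% | 14.3% | 18.5% |

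For example, m = 5% and k = 5 gives 1 − 0.95⁴ = 1 − 0.8145 = 18.5%.

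**Weight of one subject.** With the planned minimum of 92 children and 16 adolescents on mirabegron (Protocol 9.1, SAP 3), one moved subject is 1/92 = 1.1 percentage points or 1/16 = 6.3 points. These are planned randomised numbers. The safety tables use the safety analysis set, and SAP 6.1 generally bases category percentages on subjects without missing data, so the actual denominators may differ. The one-directional effect is therefore claimed for the count of severe subjects, not for the percentage.

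**Relationship: does the table agree with SAP 5.4.1?** Take five example subjects.

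| Records | SAP 6.5.1 row | Drug-related under 5.4.1? | Highest non-missing relationship |
|---|---|---|---|
| related, missing | missing | yes | related |
| related, not related | related | yes | related |
| not related, missing | missing | yes | not related |
| missing only | missing | yes | missing |
| not related, not related | not related | no | not related |

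Under SAP 6.5.1, related (1) + missing (3) = 4, which equals the 4 subjects drug-related under 5.4.1. This holds in general: a subject is in one of those two rows exactly when at least one record is related or unassessed, and that is the 5.4.1 definition. Under a highest-non-missing rule, related (2) + missing (1) = 3, and the agreement is lost through the third subject.

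**The case against.** The strongest case against the point has three parts.

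- **The severe event is not hidden.** It stays under severe in the event count of the same summary and in the listings. The serious-TEAE and discontinuation tables do not depend on the severity grade. This stands, and it limits the point to the subject counts by severity.
- **The protocol is silent on missing grades.** Its sentence concerns the same AE recorded more than once, so it does not reach an SOC row that pools different events. This stands for SOC rows. At PT level the protocol rule applies directly and has no exception, so the departure there remains.
- **Missing grades should be rare.** Protocol 12.4.4 has the investigator grade each AE, Protocol 12.4.3 requires a causality assessment for each one, and SAP 1 provides a data review before hard lock. This also stands as to size. It does not defend the rule, which does nothing when no grade is missing and misplaces subjects when a graded and an ungraded record share a row.

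A reader might go further and infer that the exception contradicts SAP 5.4.1, or that subjects with related events drop out of the drug-related tables. The documents do not support that. SAP 5.4.1 includes events "or with missing assessment of the causal relationship" in the drug-related definition, so those subjects remain in the overview and in the drug-related SOC and PT tables. The related and missing rows of the by-relationship table add up to the same count.

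**Conclusion.** The point holds for severity. In the subject counts by severity, for all TEAEs and for drug-related TEAEs, SAP 6.5.1 reports a subject as missing when any record in the SOC or PT row lacks a grade, even if another is severe. The count of severe subjects can only fall as a result, and at PT level the rule departs from Protocol 9.5.1.

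The size is unknown and probably small. It rests on a missing-grade rate that the documents do not give. The 1.0% to 18.5% range assumes 1% to 5% missing per event, independence between events, and two to five events in the row, one of them severe. It is the chance for one such subject, not a predicted shift in the table.

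For relationship there is no contradiction to correct. The related row read alone is lower than the drug-related count, but the related and missing rows together match it exactly.

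**What to change.** Replace the exception in SAP 6.5.1 with a sentence to this effect: each subject is counted at the worst non-missing severity within the SOC or PT, and as missing only when all of that subject's records in that SOC or PT lack a grade. Apply the same sentence to drug-related TEAEs by severity.

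For relationship a change is optional. If direct agreement with the drug-related tables is wanted, count missing causality as related in the by-relationship table, as SAP 5.4.1 does. Do not adopt the highest non-missing relationship on its own, because it breaks the present match.

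The cost is one sentence and a small program change. No new data are needed, efficacy is untouched, and SAP 1 allows revisions before database hard lock. If no grades turn out to be missing, the tables are unchanged.

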6.5.2 Clinical Laboratory Evaluation

The baseline value will be the last non-missing value taken on or prior to first dose of study drug.

Quantitative clinical laboratory variables, i.e., hematology, biochemistry, and urinalysis will be summarized using mean, standard deviation, median, minimum and maximum, for each age group and overall, by treatment group and visit.

Summary of laboratory values will be presented for visit 1, 3, 5, 7 and 8 (EoS)], and for EoT values.

Additionally, a within-subject change will be calculated as the post-baseline measurement minus the baseline measurement and summarized in the same way. Each laboratory result will be classified as low (L), normal (N), or high (H) at each visit according to the laboratory supplied reference ranges.

The number and percentage of subjects below and above reference range will be summarized, for each age group and overall, by treatment group and visit.

Frequency tabulations of qualitative clinical laboratory variables (urinalysis) will be presented, for each age group and overall, by treatment group and visit.

Shifts from baseline to week 4, week 12 and EoT will be summarized by two types of shift tables:

- Shift tables of reference range (low, normal, high) changes from baseline to week 12 and to EoT, and
- Summary shifts of reference range changes from baseline to week 4, week 12 and EoT.

These shifts are categorized as:

- "Shift to Low": shift from normal or high to low
- "Shift to High": shift from normal or low to high
- "Categorized Increase": shift from low to normal or from normal to high
- "Categorized No Change": value stays in the same reference range
- "Categorized Decrease": shift from high to normal or from normal to low.

All clinical laboratory data collected during the study and variables derived from it will be listed using SAF.

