7.2.2 Laboratory Assessments

Blood samples for hematology and biochemistry and urine samples for urinalysis will be collected as indicated in the Schedule of Assessments [Table 1]. All clinical laboratory assessments will be performed at a central laboratory except for urinalysis dipsticks which will be conducted locally to support study eligibility or AEs. A urine pregnancy test in female subjects of childbearing potential will be performed at all on-site visits. A topical anesthetic cream or plaster must be offered at the point of venipuncture to minimize distress of the subject. For sampling the arm opposite to the arm used for blood pressure measurements should be used (i.e., preferably the left arm). Blood sampling should occur after vital signs and ECG measurements.

Sample collection, handling and storage will be described in a laboratory manual. All clinical laboratory test results, including ULNs used in exclusion and discontinuation criteria, will be compared to age appropriate norms.

Sponsor: APGD EudraCT number 2016-001767-37 - CONFIDENTIAL -

ponsor: APGD ISN/Protocol: 178-CL-204

Scheduled blood sampling will only be performed at screening (visit 1), week 4 (visit 5) and EoT (visit 7) to keep the burden to subjects at a minimum. Additional hematology, biochemistry and urinalysis (urinalysis dipstick) tests will be performed at visit 3/week 0 (baseline) and visit 8/week 14 (EoS) only if an AE related to hematology, biochemistry or urinalysis parameters occurred since the previous visit or at the discretion of the investigator. If any of the clinical laboratory tests results are outside the normal range at any scheduled time point during the study, the investigator may decide to repeat the test(s) on new samples. The clinical relevance of the abnormal results will be documented. Clinically relevant changes will be recorded as AEs (see [Section 7.3 Adverse Events and Other Safety Aspects]).

Refer to the Alternate Schedule of Assessments [Table 12] for acceptable alternate methods to assess safety and efficacy parameters in the event the study is interrupted due to a crisis (e.g., natural disaster, pandemic).

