5.4.3 Clinical Laboratory Variables

Hematology, biochemistry and urinalysis assessments will be taken at visit 1/week -4 (screening), visit 5/week 4, and visit 7/week 12 (EoT). Additional hematology, biochemistry and urinalysis tests will be performed at visit 3/week 0 (baseline), and visit 8/week 14 (EoS) only if an AE related to hematology, biochemistry or urinalysis parameters occurred since the previous visit or at the discretion of the investigator.

All clinical laboratory assessments will be performed at a central laboratory or at a local laboratory if results can be made available to the investigative site (see protocol, Appendix 12.23, Table 11), except for urine pregnancy testing and urinalysis (urinalysis dipstick), which will be performed at a local laboratory. Pregnancy test in females of child bearing potential will be performed in serum at screening, at baseline, visit 5/week 4, visit 7/week 12 (EoT), and visit 8/week 14 (EoS).

Additional hematology, biochemistry and urinalysis (UA dipstick) tests will be performed at visit 3/week 0 (baseline), visit 5/week 4 and visit 8/week 14 (EoS) only if an AE related to hematology, biochemistry or urinalysis parameters occurred since the previous visit or at the discretion of the investigator. If any of the clinical laboratory tests results are outside the normal range at any scheduled time point during the study, the investigator may decide to repeat the test(s) on new samples. The clinical relevance of the abnormal results will be documented. Clinically relevant changes will be recorded as AEs (see Section 7.3 of protocol: Adverse Events and Other Safety Aspects).

The laboratory parameters that will be assessed during the conduct of the study are listed in Table 5.

Hematology	Biochemistry	Urinalysis			
Hematocrit	Albumin	Leukocyte esterase			
Hemoglobin	Alanine aminotransferase	Nitrites			
Mean corpuscular volume	Alkaline phosphatase	pH			
Mean corpuscular hemoglobin	Aspartate aminotransferase	Protein			
Mean corpuscular hemoglobin	Bicarbonate	Red blood cells			
concentration	Blood urea nitrogen				
Platelets	Calcium				
Red blood cell count	Chloride				
White blood cell count	Corrected serum calcium				
White blood cell count differential	Creatinine				
	Creatinine kinase				
	Glucose				
	Lactate dehydrogenase				
	Magnesium				
	Phosphate				
	Potassium				
	Serum hCG for female subjects				
	Sodium				
	Total bilirubin (total and direct)				
	Total protein				

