6 STATISTICAL METHODOLOGY

6.1 General Considerations

Efficacy data will be summarized for each age group (children [5 to <12 years of age] and adolescents [12 to <18 years of age]) by treatment group and visit, and safety data will be summarized for each age group and overall, by treatment group and visit, unless otherwise specified.

In general, continuous data will be summarized descriptively including the number of subjects (n), mean, standard deviation (SD), median, minimum and maximum. Categorical data will be summarized by frequencies and percentages. Percentages by categories will be based on the number of subjects with no missing data, i.e. the percentages for the non-missing categories will add up to 100%.

All statistical comparisons will be conducted using 2-sided tests at the 10% significance level unless stated otherwise. All null hypotheses will be of no treatment difference, all alternative hypotheses will be two-sided, unless specifically stated otherwise.

All data summarization and analyses will be performed using SAS® Version 9.4 or higher on Red Hat Enterprise Linux. Specifications for table, figure, and data listing formats can be found in the TLF specifications.

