6.5.2.1 Central and Local Laboratory Data

In this study laboratory data may come from a central laboratory or a local laboratory, see Table 12 of the protocol.

For summarizing the data of a laboratory parameter the data from the local laboratory will be transformed. First all data from the parameter assessed in the local laboratory will be transformed into SI units. Next local laboratory data will be transformed according to the transformation formula below. Let x be the value of the laboratory parameter from the local laboratory, ULNL the upper limit of the normal range of the local laboratory, and ULNC the upper limit of the normal range of central laboratory then the transformed value (t) from the local laboratory is:

$$t = x.\frac{ULNC}{ULNL}$$
 (Scale normalization, Karvanen et al.)

This value t will be used for reporting laboratory values.

The results from the local laboratory will be used to determine whether a result is outside the normal range.

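### Laboratory tables treat selectively sampled visit 3 and 8 blood results as scheduled visits, state two baseline rules, and rescale local results by the upper limit alone

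*SAP*

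**What the plan says.** **Sampling.** Protocol 7.2.2: "Scheduled blood sampling will only be performed at screening (visit 1), week 4 (visit 5) and EoT (visit 7"). At visits 3 and 8, SAP 5.4.3 has tests done "only if an AE related to hematology, biochemistry or urinalysis parameters occurred since the previous visit or at the discretion of the investigator". Footnote i of the protocol's Table 1 says the same.

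**Tabulation.** SAP 6.5.2: "Summary of laboratory values will be presented for visit 1, 3, 5, 7 and 8 (EoS)], and for EoT values". Values and changes are summarised by treatment group and visit, and "The number and percentage of subjects below and above reference range will be summarized, for each age group and overall, by treatment group and visit". Nothing qualifies visits 3 and 8. SAP 6.1 sets the denominator: "Percentages by categories will be based on the number of subjects with no missing data".

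**Baseline.** SAP 6.5.2 takes the most recent available value up to the first dose. SAP 5.4.3 takes visit 1 for changes and shifts, with a fallback if it is missing. Table 10 in SAP 6.10.1 labels laboratory results from Day -7 until the first dose as Baseline.

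**Local results.** SAP 6.5.2.1 converts a local result x to SI units and then to t = x × ULNC/ULNL, with "ULNL the upper limit of the normal range of the local laboratory, and ULNC the upper limit of the normal range of central laboratory". Then: "This value t will be used for reporting laboratory values". The same section decides out-of-range status from the local result. SAP 6.5.2.2 bases the liver criteria on central data. Local blood testing comes from the crisis schedule in protocol Appendix 12.13, Table 12.

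**Urinalysis.** Footnote i makes the visit 3 and 8 tests conditional. However, exclusion 32, applied at visit 3, needs a dipstick result from every subject, and protocol 2.3 describes urinalysis at each clinic visit.

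**The concern.** The visit 8 rows will stand beside weeks 4 and 12 in the same table, by arm. Weeks 4 and 12 are meant to cover everyone. Visit 8 covers whoever had a laboratory-related event or was tested at the investigator's choice, and that selection happens after randomisation. A reader following the columns would take a change in who was tested for a change over time.

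Visit 3 matters for another reason. Under the 6.5.2 rule, a triggered visit 3 value replaces the visit 1 value as baseline for those subjects only. Selection then enters their changes and shifts at every later visit. Under the 5.4.3 rule it does not. The SAP states both.

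The conversion rule uses no lower limit. For analytes with a two-sided range, such as potassium, sodium and hemoglobin, it can report a number on the wrong side of the central lower limit next to a flag that says normal. Where a subject's baseline is central and a later sample is local, part of the reported change comes from the conversion.

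**Working it through.** **1. Which draws are scheduled.** Protocol Table 8 lists two pharmacokinetic samples of 5.0 mL and three laboratory samples of 4.5 mL:

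- 2 × 5.0 + 3 × 4.5 = 23.5 mL, the stated total.
- Adding two conditional draws: 23.5 + 2 × 4.5 = 32.5 mL, the stated maximum.

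Both figures reproduce exactly, so three laboratory draws are scheduled (visits 1, 5 and 7) and visits 3 and 8 are the extras.

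**2. Effect of the denominator at visit 8.** The documents give no retest rate, so these inputs are assumptions. Let q be the fraction tested, pS the fraction abnormal among the tested and pU the fraction abnormal among the untested. The table shows pS; the whole arm has q·pS + (1 − q)·pU.

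- 4 of 92 tested, 3 high, all untested in range: table 3/4 = 75%; arm 3/92 = 3.3%.
- q = 10%, pS = 50%, pU = 5%: table 50%; arm 0.10 × 0.50 + 0.90 × 0.05 = 9.5%, with 92 × 0.10 ≈ 9 children in the row.
- q from 5% to 20% and pS from 30% to 80%, with pU = 5%: table 30% to 80%; arm from 0.05 × 0.30 + 0.95 × 0.05 = 6.3% to 0.20 × 0.80 + 0.80 × 0.05 = 20%.

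**3. When the upper-limit ratio is exact.** It sends ULNL to ULNC and LLNL to LLNL × ULNC/ULNL. The second equals LLNC only if both lower limits are zero or LLNC/LLNL = ULNC/ULNL.

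**4. Numerical illustration.** The documents contain no reference ranges, so all ranges are assumed. The two-limit form is t = LLNC + (x − LLNL)(ULNC − LLNC)/(ULNL − LLNL).

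| Analyte | Local range | Central range | x | x × ULNC/ULNL | Two-limit form |
|---|---|---|---|---|---|
| Potassium | 3.5–5.5 | 3.5–5.0 | 3.6 | 3.27 | 3.58 |
| Sodium | 136–148 | 135–145 | 140 | 137.2 | 138.3 |
| Sodium | 136–148 | 135–145 | 136 | 133.2 | 135.0 |
| Hemoglobin (g/L) | 115–155 | 115–145 | 120 | 112.3 | 118.8 |

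For example, 3.6 × 5.0/5.5 = 3.27, and 3.5 + 0.1 × 1.5/2.0 = 3.575. Each x is normal locally. Potassium 3.6, sodium 136 and hemoglobin 120 are reported below the central lower limit, while the flag, taken from the local result, says normal.

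The distortion is not universal. With ranges 0–50 local and 0–40 central, the ratio maps the range exactly. With 150–450 local and 130–400 central, the local lower limit becomes 150 × 400/450 = 133.3, and no locally normal value falls below 130.

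**The case against.** **Visits 3 and 8.** The summaries are descriptive and show n, so a row with n = 4 beside rows near 90 partly discloses itself. All laboratory data are listed anyway. Visit 8 does not enter the shift tables, which stop at week 12 and EoT. Nor does it enter the EoT carry-forward, which excludes data from more than 5 days after the last dose, while visit 8 falls at least 14 days after EoT. All of this stands and limits the consequence. It does not make a visit 8 mean or percentage comparable with week 12, because showing n does not tell the reader how those subjects were chosen.

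A reader might infer that these samples come only from children with abnormal results. The documents do not support that, because investigator discretion is a separate trigger. Nor can visit 3 show worsening after treatment, since it precedes dosing. One might also infer that week 4 is conditional, from a second paragraph in SAP 5.4.3: "Additional hematology, biochemistry and urinalysis (UA dipstick) tests will be performed at visit 3/week 0 (baseline), visit 5/week 4 and visit 8/week 14 (EoS"). The first paragraph of that section, protocol 7.2.2 and the blood volumes all make week 4 scheduled.

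**Rescaling.** The SAP contains most of the effect. Flags, and the shift tables built on them, use local results, and the liver criteria use central data. Local blood testing needs a crisis and discussion with the medical monitor. A reader might infer a spurious drug effect on electrolytes or hemoglobin. Treatment is randomised and double-blind, and a crisis acts on countries, sites or participants and not on arms, so added error is the expected result. It would also be too strong to say the ratio is valid only with zero lower limits, since proportional limits suffice.

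The two-limit form can itself fail far below range. With assumed ranges local 10–30 and central 5–55, x = 5 gives 5 + (5 − 10) × 50/20 = −7.5. It therefore needs a safeguard.

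**Conclusion.** The point holds in limited form, for safety summaries only. The primary efficacy analysis is untouched.

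Hematology and biochemistry rows at visit 8 describe a selected subset. Under one of the SAP's two baseline rules, triggered visit 3 values carry that selection into changes and shifts for the affected subjects. This follows from the text. How far the percentages mislead depends on retest rates that the documents do not give, so the percentages above are illustrations.

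The upper-limit ratio can report a locally normal value below the central lower limit beside a normal flag, where lower limits are non-zero and not proportional to the upper limits. This affects only continuous summaries and listings of locally analysed samples. Its size cannot be computed without reference ranges and the number of local samples.

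The conclusion about visits 3 and 8 does not extend to urinalysis, because the documents conflict on whether urine is tested there in everyone.

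**What to change.** 1. **SAP 6.5.2:** remove visits 3 and 8 from the by-visit hematology and biochemistry summaries. List those results, or tabulate them separately with n as event-triggered or discretionary samples.
2. **SAP 5.4.3, 6.5.2 and Table 10:** state one laboratory baseline rule. Visit 1, as in 5.4.3, applies the same rule to all subjects. Make this change together with the first, so that changes are not computed from visit 3 values that no longer appear in the table. Correct the 5.4.3 paragraph that lists visit 5 as conditional.
3. **Urinalysis:** reconcile footnote i with exclusion 32 and protocol 2.3 before altering any visit 3 urinalysis summary on this ground.
4. **SAP 6.5.2.1:** for analytes with a non-zero lower limit, use t = LLNC + (x − LLNL)(ULNC − LLNC)/(ULNL − LLNL). Leave any negative result out of the continuous summaries and list it untransformed. Keep the upper-limit ratio where the lower limit is zero.

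The cost is SAP wording and a little more programming. The lower limits are already needed for the low/normal/high classification. Visit 3 and 8 blood results would appear only in listings or a separate table, and no data are lost.
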